2.3.2 Safety population

The safety population includes all randomized patients who received at least one dose of the study drug. Analysis of the Safety population will be done according to the treatment received (as treated).

In addition:

- Nonrandomized but treated patients will not be part of the safety population; however, their safety data will be presented separately
- Randomized patients for whom it is unclear whether they took the IMP will be included in the safety population as randomized
- For patients receiving more than 1 IMP during the trial, the treatment group allocation for as-treated analysis will be the treatment group for which the patient received the first dose.

In such cases, individual patient listings will be provided for each treatment group with treatment start and end date for each treatment exposed.

2.3.3 PK population

The PK analysis population includes all patients who received any study drug and who had at least 1 non-missing serum concentration available for PK analysis following the first dose of study drug.

2.3.4 ADA population

The ADA population includes all patients who had at least 1 post-baseline valid ADA sample following the first dose of study drug.

2.4 STATISTICAL METHODS

2.4.1 Demographics and baseline characteristics

Continuous data will be summarized using the number of available data, mean, standard deviation (SD), median, minimum, and maximum for each treatment group. Categorical and ordinal data will be summarized using the number and percentage of patients in each treatment group.

Parameters will be summarized based on the mITT populations.

Parameters described in [Section 2.1.1](#) will be summarized by treatment group and overall treatment groups using descriptive statistics.

Medical and surgical history will be summarized by SOC and PT sorted by internationally agreed order of SOC and by the decreasing frequency of PT within SOC in total group (including all the randomized patients). P-values on demographic and baseline characteristic data will not be calculated.

No specific description of the safety parameters will be provided at baseline. If relevant, the baseline values will be described along with each safety analysis.

2.4.2 Concomitant medications

Concomitant medications will be summarized by treatment group according to the WHO-DD dictionary, considering the first digit of the anatomic category (ATC) class (anatomic category) and the generic names. All ATC codes corresponding to a medication will be summarized. Patients will be counted once in each ATC category (anatomic or therapeutic) linked to the medication; therefore, patients may be counted several times for the same medication.

Investigational medications are not coded, a category 'Investigational medications' will be used for these medications if applicable. The tables for concomitant medications will be sorted by

decreasing frequency of anatomic category followed by all other generic names based on the incidence of the total group (including all the randomized patients). In case of equal frequency regarding anatomic categories (respectively, generic names), alphabetical order will be used.

A listing of rescue medications will be provided including the following information:

- Start and end dates
- WHODD Preferred term
- Dose, unit and route
- ATC level 2 and ATC level 4

2.4.3 Extent of investigational medicinal product exposure and compliance

2.4.3.1 Extent of investigational medicinal product exposure

Patients will receive a single dose of study drug on Day 1. Patients may receive a second dose with study drug (based on the original treatment group assigned) 24 to 48 hours after the first dose, if they meet prespecified criteria.

Duration of IMP exposure will be analyzed by summarizing the number of doses patient received by treatment group in the safety population.

A listing will be provided for all study drug administered including the following information:

- Infusion rate (units: mL/h)
- Side and location of drug administration
- Start and end time
- Duration of intravenous infusion
- total dose injected (yes/no)
 - If no and not related to any AE, reason for not administration of total planned dose (Device problem, patient decision, other)
- Evidence of infusion reaction
- infusion interruptions
 - If yes, whether re-administered (yes/no)

2.4.3.2 Compliance

The percentage of compliance, defined as the number of patients who fully completed infusion of the first study drug divided by number who received study drug, will be presented by treatment group based on the safety population.

2.4.4 Analyses of efficacy endpoints

Table 3 below summarizes the analyses for each type of efficacy endpoints in general.

Table 3 – Summary of analyses for each type of efficacy endpoint

Type of endpoint	Statistical method	Graphical presentation
Time-to-event	Log-rank test (stratified) Cox-PH model (stratified)	KM curve
% of patients over time	CMH test (stratified) Descriptive statistics	Bar plot over time
% of patients at end	CMH test (stratified) Descriptive statistics	Bar plot
Continuous variable over time	ANCOVA model Descriptive statistics	Line plot over time
Continuous variable at end	ANCOVA model Descriptive statistics	Histogram

For time to event analysis, the time to event duration is calculated as:

$$\text{Date of first occurrence/episode of the event} - \text{date of first dose} + 1.$$

2.4.4.1 Analysis of primary efficacy endpoint(s)

The primary efficacy analysis will be pairwise comparisons between sarilumab doses (400 mg and 200 mg) and placebo with respect to the primary endpoint, time to improvement of 2 points in clinical status assessment from baseline using the 7-point ordinal scale, using a log-rank test stratified by randomization stratum with treatment as a fixed factor in the mITT population. P-values for the pairwise comparison of each sarilumab dose versus placebo will be provided.

Hazard ratios for the estimation of treatment effect of each sarilumab dose compared to placebo will be provided using Cox proportional hazards model stratified by the randomization stratum with treatment as a covariate, along with 2-sided confidence intervals. Kaplan-Meier (KM) plot and the median time-to-improvement of 2 points will also be provided by treatment groups.

Superiority of sarilumab over placebo will be declared if the null hypothesis is rejected at the 5% (2-sided) significance level following the multiplicity control procedure specified in [Section 2.4.4.3](#).

Patients who have an improvement of 2-points in clinical assessment or discharge (other than death) will be considered as events, while patients who do not experience improvement of 2-points will be censored at the last observation time point. Patients who take rescue medication in the study without improvement of 2-points before that will be censored at the date of rescue medication started.

In addition, the proportion of patients with at least 2-point improvement from baseline at each day post-baseline will be provided using descriptive statistics. Graphical presentations (bar charts) will be used to examine trends over time.

The analyses using the log-rank test and Cox PH model specified above will be repeated for the severe patients and critical patients at baseline as recorded on CRFs.

Baseline clinical status is defined as the worse (lower) value of screening visit and Day 1 prior to dosing. If there is a tie, flag Day 1 as baseline. Baseline values are 2, 3, 4, 5, or 6. Values 1 and 7 do not apply (if 1 or 7 appear, then data query is needed.)

Post-baseline clinical status values range from 1 through 7 on ordinal scale and data will be as recorded on the ordinal scale eCRF.

Handling of death or discharge on clinical status assessment (post-baseline)

For patients who die, the clinical status recorded on the day of death will be replaced with “1=Death” and this value will be carried forward for all subsequent study days until end of study (Day 60). Death date may be obtained from Adverse Events or Disposition CRFs or phone call at Day 60 (end of study).

For patients who discharge early (other than death), the clinical status recorded on the earliest hospital discharge date will be replaced with 7 (not hospitalized), and this value will be carried forward for all subsequent study days until end of study (Day 60). Hospital discharge information (discharge date and discharge reason) may be obtained from the Discharge Reason eCRF. If there is subsequent hospitalization, the clinical status will not be replaced by 7 after the second hospitalization.

Handling of missing data on clinical status assessment (post-baseline)

For patients who are alive and not discharged (ie, still hospitalized), missing clinical status value (ordinal scale) on a given study day will be imputed using data on the type of oxygen delivery device used by the patient on that day (last type of device used if multiple types were used in a day).

Clinical status = 2 (if using invasive mechanical ventilation or ECMO), or
= 3 (if using non-invasive mechanical ventilation or high-flow nasal cannula), or
= 4 (if using nasal cannula, simple face mask, or non-rebreather face mask) or
= 5 (if not using supplemental oxygen)

Sensitivity analysis

The PPS and ITT will be used for sensitivity analysis of the primary efficacy endpoint, as described above.

Subgroup analyses

Descriptive analyses will be performed on the primary endpoint to summarize the treatment effect of each sarilumab dose versus placebo by the following variables:

- Age (<median, >=median)
- Age group (≥ 18 and < 64 , ≥ 65 and < 84 , ≥ 85 years)
- Sex (Male, Female)
- Race (White, Black or African American, Asian, Other). Note: Japanese will be grouped with Asian, a group with less than 5 patients in any treatment may be grouped with 'Other'
- Ethnicity (Hispanic or Latino, Not Hispanic or Latino)
- Severity of illness (per IRT) (Severe, Critical)
- Severity of illness (as recorded on CRFs) (Severe, Critical)
- Systemic corticosteroids use (per IRT) (Yes, No)
- Systemic corticosteroids use (as recorded on CRFs) (Yes, No)
- Fever status at baseline (Yes, No)
- Pneumonia present based on historical chest X-Ray, CT scan or MRI or lung auscultation (Yes, No)
- Any symptom of Fever, Cough, or Dyspnea (Yes, No)
- Time from dyspnea onset to baseline (≤ 5 days, > 5 days). Note: patients with no dyspnea will be classified as ≤ 5 days
- SpO₂/FiO₂ ratio (<median, >=median)
- CRP level (<median, >=median)
- Duration of hospitalization prior to first dose (< 7 days, ≥ 7 days);
- Number of study drug administration (1, 2)

Additional subgroups may be added as needed. The treatment effects will be estimated using hazard ratio (sarilumab compared to placebo) in the subgroups using the same analysis model as for the primary efficacy endpoint as described previously (without stratification factor for the stratification-related subgroups). In addition, p-value for the interaction of treatment by subgroup effect will be provided. Graphical presentation of the results (ie, forest plot) for each sarilumab dose versus placebo will also be provided.

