Patients will be assessed daily while hospitalized. Discharged patients will be contacted by telephone on Day 29 to assess status and occurrence of re-admission to a hospital. Patients will undergo a series of efficacy, safety and laboratory assessments while in the hospital. Serum IL-6 and other markers will be collected and analyzed in a central laboratory. Nasopharyngeal (NP) samples to monitor viral infection and blood samples will be requested on day 1 (pre-dose), 4, 7, 15, 29 (or up until the day of discharge if the patient is discharged from the hospital before day 29).

Randomization will be stratified by:

- Severity of illness
  - Severe disease
  - Critical disease
- Systemic corticosteroids (Yes/No)

The severity categories are:

- Severe disease:
  - Requires supplemental oxygen administration by nasal cannula, simple face mask, or other similar oxygen delivery device
- Critical disease:
  - Requires supplemental oxygen requiring delivered by non-rebreather mask or high-flow nasal cannula
  - OR Use of invasive or non-invasive ventilation,
  - OR Requiring treatment in an intensive care unit.

Note: Participants meeting criteria for both severity categories will be stratified according to the more severe category.

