1.3 DETERMINATION OF SAMPLE SIZE

[figure not shown]
The sample size calculations are performed based on the primary endpoint, the time to improvement of 2 points in clinical status assessment from baseline using the 7-point ordinal scale.

Assuming that accrual duration is 3 months (~90 days) with each patient followed for a period of at least 29 days, the proportions of patients with two points improvement from baseline in clinical status assessment at Day 15 are 45% and 70% for placebo and sarilumab, respectively, a total sample size of approximately 400 patients with a 2:2:1 randomization ratio provides at least 90% power for pairwise comparisons between each sarilumab dose (400 mg IV or 200 mg IV; n~160 each) and placebo (n~80), using a log-rank test of superiority at a two-sided significance level of 0.05. Sample size calculation was performed using PASS 14.

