2.4.4.2 Analyses of secondary efficacy endpoints

Key secondary endpoint

The percentage of patients alive at Day 29 will be analyzed using Cochran-Mantel-Haenszel (CMH) test stratified by randomization strata of severity of illness and corticosteroid use in the mITT population. The difference in proportions of patients for each Sarilumab dose compared to placebo (sarilumab - placebo), along with associated 2-sided 95% confidence levels, and p-value will be provided.

Superiority of sarilumab over placebo will be declared if the null hypothesis is rejected at the 5% (2-sided) significance level following the multiplicity control procedure specified in [Section 2.4.4.3](#).

In addition, bar plot for the proportion of patients alive at Day 29, KM curves for the overall survival will be provided by treatment group. Hazard ratios for the estimation of treatment effect of each sarilumab dose compared to placebo will be provided using Cox proportional hazards model stratified by the randomization stratum with treatment as a covariate, along with 2-sided confidence intervals.

These analyses will be repeated for the severe patients and critical patients at baseline as recorded on CRFs.

Other secondary endpoints

Details for analyses and derivation of the variables associated with the other secondary endpoints specified in [Section 2.1.3.2](#) are detailed below.

7-point ordinal scale

The percent of patients with each category of the 7-point ordinal scale observed value at each day will be summarized using descriptive statistics. Graphical presentations (stacked bar charts) will also be used to examine trends over time.

Analysis of endpoint #1: proportion of patients with one-point improvement from baseline

Proportion of patients with at least 1-point improvement from baseline at Day 4, 7, 15, 21, and 29 will be analyzed using the same analysis model as for the key secondary endpoint as described previously. Graphical presentations (bar charts) will be used to examine trends over time.

Analysis of endpoint #2: Mean change in 7-point ordinal scale from baseline

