Changes from baseline in the 7-point ordinal scale for Day 4, 7, 15, 21, 29 (or until discharge) will be analyzed using an ANCOVA model with treatment group and randomization strata as fixed effects and baseline value as a covariate. The least squares (LS) treatment mean difference from placebo with standard error, along with corresponding 95 % confidence interval and p-value will be provided. Graphical presentations (line plot with mean and error bar) will also be used to examine trends over time using mean values (\pm SE) and mean changes from baseline (\pm SE).

The 7-point ordinal scale at each day and their changes from baseline will also be summarized for each treatment group through descriptive statistics including mean, median, standard deviation, minimum and maximum.

Fever

Body temperature is collected using varying methods (the routes in eCRF are axillary, auricular, oral, rectal) at multiple timepoints each day.

Baseline body temperature is defined as the highest temperature at any time prior to first dose.

Post-baseline body temperature is defined as the highest temperature from each day among all temperatures from different timepoints (morning, evening, etc).

Patients body temperature and its change from baseline will be summarized at each day by treatment group by timepoint over the study period. Graphical presentations (line plot with mean and error bar) will also be used to examine trends over time using mean values (\pm SE) and mean changes from baseline (\pm SE).

All temperatures will be converted to oral values as following:

- Rectal/Auricular subtract 0.6 deg C = Oral deg C
- Axillary add 0.6 deg C = Oral deg C

Analysis of endpoint #3: time to resolution of fever

Resolution of fever is defined as body temperature ($\leq 36.6^{\circ}\text{C}$ [axilla], or $\leq 37.2^{\circ}\text{C}$ [oral], or $\leq 37.8^{\circ}\text{C}$ [rectal or auricular]) for at least 2 consecutive days without antipyretics or until discharge, whichever is sooner.

The analysis will be performed similarly to the primary endpoint.

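### The primary and Day 29 survival analyses never adjust for the baseline ordinal score, although the critical stratum mixes scores 2 to 4; the tests are valid, and adjustment would be a cheap, modest gain.

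*SAP*

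**What the plan says.** SAP 2.4.4.1 compares each dose with placebo "using a log-rank test stratified by randomization stratum with treatment as a fixed factor in the mITT population". The Cox model for the hazard ratio uses the same strata, with treatment as its only covariate. SAP 2.4.4.2 tests Day 29 survival by CMH, "stratified by randomization strata of severity of illness and corticosteroid use in the mITT population", and reports a difference in proportions. Protocol 9.4.2 and 9.4.3.1 specify the same two tests, and the protocol synopsis repeats them.

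Severity has two levels. One route into the critical level (Protocol 4.1) is: "Requires supplemental oxygen requiring delivered by non-rebreather mask or high-flow nasal cannula". The others are invasive or non-invasive ventilation, or ICU need alone.

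The baseline score is used as a covariate elsewhere. The ANCOVA of mean change in the same scale (SAP 2.4.4.2, endpoint #2) has "treatment group and randomization strata as fixed effects and baseline value as a covariate".

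Sensitivity analyses of the primary endpoint change only the population (PPS, ITT). The primary subgroup list includes age, severity and SpO2/FiO2, but not the baseline ordinal score. Both confirmatory analyses are repeated in severe and in critical patients.

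**The concern.** The baseline score is more than an ordinary optional covariate, because it sets what counts as an event. A ventilated patient at score 2 succeeds on reaching 4, still on oxygen. A patient at 4 must be off oxygen with no ongoing care need, or be discharged. Within the critical stratum these patients are compared as if they faced the same event, and repeating the analysis in critical patients leaves them mixed.

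Two things are at stake. One is efficiency, if the true effect is smaller than planned, and for mortality, for which no power is stated. Mortality is step 2 of the hierarchy (SAP 2.4.4.3), so it also gates the 200 mg tests. The other is interpretation: if the arms differ by chance in their share of ventilated patients, no prespecified analysis would show how far that drove the result.

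**Working it through.** **1. The plan's own power.** Inputs from SAP 1.3: improvement "at Day 15 are 45% and 70% for placebo and sarilumab, respectively"; sizes "400 mg IV or 200 mg IV; n~160 each) and placebo (n~80"; "using a log-rank test of superiority at a two-sided significance level of 0.05". Exponential times are assumed.

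- Hazard ratio = ln(0.30)/ln(0.55) = 2.01, and ln(2.01) = 0.700.
- Events by Day 15 = 80×0.45 + 160×0.70 = 36 + 112 = 148.
- Schoenfeld power = Φ(√(d × 1/3 × 2/3) × ln HR − 1.96). With d = 148: √32.9 = 5.73; 5.73×0.700 − 1.96 = 2.05; power 98.0%.
- With 29 days each: daily hazards 0.598/15 = 0.0399 and 1.204/15 = 0.0803; events = 80×0.685 + 160×0.9025 = 199; power 99.7%.
- With 90 days' accrual plus 29 days: 231 events, 99.9%.
- Other methods: Freedman 93.4% (15 days) and 98.1% (29 days); two proportions at Day 15, 96.4%.

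The SAP's claim that the size "provides at least 90% power for pairwise comparisons between each sarilumab dose" is therefore reproduced as a lower bound. With 29 days' follow-up, 90% power needs only a hazard ratio of about 1.65 (62.6% v 45%), and 80% needs about 1.54 (60.2% v 45%).

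**2. What the critical stratum contains.** The device mapping is the SAP's rule for missing post-baseline status (2.4.4.1), the most explicit link it gives between device and score.

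| Critical patient on | Score | A 2-point gain means |
|---|---|---|
| Invasive ventilation | 2 | reaching 4 |
| Non-invasive ventilation or high-flow cannula | 3 | reaching 5 |
| Non-rebreather mask | 4 | reaching 6, or discharge |

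Because ICU need alone qualifies, and SAP 2.4.4.1 allows baseline values 2 to 6, the mix could be wider.

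**3. Effect of adjusting, 160 v 80, by simulation** (1,500 trials per primary setting, 2,000 per mortality setting). None of these inputs is in the documents:

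- Critical share 40-50%; scores 2/3/4 within critical from 15/40/45% to 50/25/25%; severe patients all at score 4; corticosteroid use 25% with no effect.
- Improvement hazard ratio v score 4: 0.8 to 0.5 for score 3, and 0.6 to 0.15 for score 2; log hazard ratio per SD of age -0.1 to -0.3.
- Death odds ratio: 1.5 to 3 for score 3, 2.5 to 8 for score 2, and 1.3 to 2.2 per SD of age.
- No deaths, rescue or dropout in the primary model.

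| Setting | Planned test | Change, Cox or logistic + score | Change, + score and age |
|---|---|---|---|
| Primary, 70% v 45% | 99.3-99.7% | within -0.2 to +0.4 | within -0.2 to +0.4 |
| Primary, 62.5% v 45% | 86.9-90.5% | -1.5 to +2.4 | -1.4 to +4.2 |
| Primary, 60% v 45% | 73.5-81.1% | -1.7 to +2.1 | -1.3 to +5.6 |
| Death, 20% v 10% | 56-59% | -0.8 to +2.4 | -0.4 to +5.7 |
| Death, 25% v 12% | 70-74% | -1.0 to +2.3 | -0.2 to +6.1 |
| Death, 15% v 8% | 39-41% | -1.4 to +0.9 | -1.0 to +3.6 |

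Changes are in percentage points. Using the score as a further log-rank stratum gave -1.0 to +3.2 in the two smaller-effect primary settings. Null rejection was 3.5-6.8% (primary) and 4.4-6.4% (mortality), with no consistent inflation for any method.

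**4. Smaller primary effects.** Further simulations at hazard ratios of 1.35 to 1.5 gave about +1 to +8 points from the score, mostly +2 to +4, and still about 97-99.7% power with or without it at the design effect. One example uses 213 v 107, half critical split 40/35/25% over scores 2/3/4, and daily hazards of 0.02/0.05/0.085. Power went from 57.5% to 61.7% (HR 1.35) and from 82.9% to 85.2% (HR 1.5). The sizes assume the 200 mg arm closes after 200 of 400 patients: 80 + 133 = 213 and 40 + 67 = 107. Read as placebo hazards, with severe patients at score 4, these rates imply about 59% improved at Day 15, not the planned 45%. The example therefore illustrates; it does not recalculate the plan.

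**5. Chance imbalance.** Take critical patients as 40-50% of the trial, with 15-50% of them at score 2. A gap between arms of at least 10 percentage points in the ventilated share of critical patients then occurs in about 16-35% of trials at 160 v 80, and in 9-28% at 213 v 107. Check at 40% critical and 50% ventilated (64 v 32 patients): SE = √(0.25×(1/64 + 1/32)) = 0.108; 0.10/0.108 = 0.92; two-sided probability about 36% by the normal approximation.

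**The case against.** The strongest reply is that this is a preference about efficiency. Both tests stratify on the randomization factors, severity already carries part of the score's information, and at the planned effect there is no power left to gain. Gains appear only at effects the plan does not assume, and some settings show a small loss. All of that stands and limits the size of the point.

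Three stronger readings are tempting, and the documents do not support them.

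- *The mortality estimate is pulled toward no effect.* That would apply to an odds ratio. The planned estimate is a difference in proportions, which under randomization is not attenuated by leaving out a covariate.
- *Age is ignored.* SAP 2.4.4.1 lists it twice as a subgroup of the primary endpoint, with an interaction p-value. It is simply not an adjustment variable.
- *The SAP contradicts itself by adjusting endpoint #2.* Baseline adjustment is routine in an ANCOVA of change and implies nothing for a log-rank or CMH test.

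A procedural objection also carries weight. The tests are written into the protocol, and Protocol 9.4 has the SAP finalized before the interim. Protocol 4.3 reports that senior management has since reviewed an unblinded interim report, and SAP section 3 includes the ordinal scale and survival in that analysis. A change of confirmatory model now could look data-driven. This shapes the fix but does not remove the point, because people conducting the study are to have no access to the interim results and can document the choice.

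**Conclusion.** The point holds as a low-cost improvement. Neither confirmatory analysis, nor any prespecified supporting analysis of those two endpoints, adjusts for the baseline score, although that score defines the primary event and varies within the critical stratum.

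A reader might infer that the planned tests are invalid or the primary comparison underpowered. Neither follows: no method showed consistent type I error inflation, and power at 45% v 70% is about 97-99.9% by Schoenfeld's formula and simulation.

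The gain is conditional. For a primary hazard ratio of about 1.35 to 1.5, the score is worth roughly -2 to +8 points of power, typically +2 to +4. For mortality, score plus age is worth about -1 to +6 points, with the upper end requiring both to be strongly prognostic. These ranges rest on the assumed case mix and prognostic strengths listed above. Protection against chance imbalance in ventilated patients is the second reason to adjust.

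**What to change.** Before unblinding, the blinded team should document in the SAP, and align in Protocol 9.4.2-9.4.3 and the synopsis:

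- **Primary:** a Cox model stratified by severity and corticosteroid use, with baseline ordinal score as a categorical covariate and a stated rule for pooling sparse levels. The covariate form avoids up to 4×5 = 20 strata with about 80 placebo patients.
- **Day 29 survival:** a logistic model with the strata, baseline score and age, reported as a standardized risk difference, with a stated fallback for separation or non-convergence.
- **Supportive:** the present stratified log-rank and CMH tests.

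If the confirmatory tests are not to change after the unblinded interim, prespecify the two models as adjusted sensitivity analyses.

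Cost: no new data, since score and age are already collected. The SAP's latest logged version (05-May-2020) predates Amendment 04 (11-Jun-2020) and still describes 2:2:1 allocation, so a revision is due anyway. The downsides are a post-interim text change that must be shown to have been made blinded, and an adjusted hazard ratio that is conditional on the score and so not the same quantity as the planned one.

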#### **9.4.2 Primary endpoint(s)**

The primary endpoint is the time to improvement of 2 points in clinical status assessment from baseline using the 7-point ordinal scale. Patient who discharged early will be considered as meeting the two points improvement criteria.

The primary endpoint will be analyzed using a log-rank test stratified by randomization stratum with treatment as a fixed factor in the mITT population. P-value for the pairwise treatment comparison versus placebo will be provided. Estimation of treatment effect of each sarilumab dose will be provided as hazard ratio (sarilumab versus placebo) using Cox proportional hazards model stratified by the randomization stratum with treatment as a covariate, along with 2-sided confidence intervals. Kaplan-Meier (KM) plot and the median time-to- improvement of 2 points will also be provided.

Superiority of sarilumab over placebo will be declared if the null hypothesis is rejected at the 5% (2-sided) significance level following the multiplicity control procedure specified in [Section 9.4.3.1](#).

Patients who have an improvement of 2-points in clinical assessment or discharge will be considered as events, while patients who do not experience improvement of 2-points will be censored at the last observation time point. Patients who die or take rescue medication in the study without improvement of 2-points before that will be censored at the earlier date of Day 29 (for the primary analysis) or rescue medication started.

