2.1.3 Efficacy endpoints

2.1.3.1 Primary efficacy endpoint(s)

The primary endpoint is the time to improvement of 2 points in clinical status assessment from baseline using the 7-point ordinal scale.

The 7-point ordinal scale is an assessment of the clinical status. The scale is as follows:

- 1. Death;
- 2. Hospitalized, on invasive mechanical ventilation or extracorporeal membrane oxygenation (ECMO);
- 3. Hospitalized, on non-invasive ventilation or high flow oxygen devices;
- 4. Hospitalized, requiring supplemental oxygen;
- 5. Hospitalized, not requiring supplemental oxygen - requiring ongoing medical care (COVID-19 related or otherwise);
- 6. Hospitalized, not requiring supplemental oxygen - no longer requires ongoing medical care

- 7. Not hospitalized

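### Any live discharge is a primary event, so an unimproved patient recorded as discharged by acute-hospital transfer or to hospice would count as a 2-point improvement

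*SAP*

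**What the plan says.** Protocol 9.4.2 deems early discharge an improvement: "Patient who discharged early will be considered as meeting the two points improvement criteria". It then defines the event: "Patients who have an improvement of 2-points in clinical assessment or discharge will be considered as events". No exception is attached to discharge. Death is handled separately: a patient who dies or takes rescue medication without a prior 2-point improvement "will be censored at the earlier date of Day 29 (for the primary analysis) or rescue medication started".

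SAP 2.4.4.1 repeats the event rule with death as the only carve-out: "Patients who have an improvement of 2-points in clinical assessment or discharge (other than death) will be considered as events". For a live discharge, "the clinical status recorded on the earliest hospital discharge date will be replaced with 7 (not hospitalized"), and the 7 is carried forward. SAP 2.4.4 dates a time-to-event outcome at its first occurrence. On readmission: "If there is subsequent hospitalization, the clinical status will not be replaced by 7 after the second hospitalization".

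Level 7 of the scale (SAP 2.1.3.1) is "7. Not hospitalized".

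The SAP names a source for the circumstances of discharge: "Hospital discharge information (discharge date and discharge reason) may be obtained from the Discharge Reason eCRF". No rule in either document uses the reason. Neither mentions transfer to another acute hospital or discharge to hospice. The sensitivity analyses of the primary endpoint (PPS and ITT) change the population and keep the event definition.

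**The concern.** Discharge serves here as a proxy for recovery. The proxy fails for a patient who leaves the site without improving. Take a patient at level 3 who is moved to another acute hospital. If the site records this as a discharge, the score goes from 3 to 7 on that day, a gain of 4 points with no change in condition, although the patient is still hospitalized.

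Hospice shows the same problem differently. An unimproved patient who dies in hospital is not an event. The same patient discharged to hospice who dies before Day 29 stays a primary success, yet counts as not alive on the key secondary endpoint. Later readmission or death changes the carried-forward score but does not remove an event already dated at first discharge.

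At stake is whether every primary event is an improvement. The imputed 7 also feeds secondary endpoints 1 and 2 in SAP 2.4.4.2.

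**Working it through.** **Reading the rule.** A patient becomes a false event only if all of these hold: no 2-point improvement so far; no rescue medication so far (otherwise censored at rescue start); departure alive; departure recorded as a discharge. The first three follow from the text. The last depends on eCRF categories that the documents do not show.

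**Inputs from Protocol 9.2 and SAP 1.3.** Improvement by Day 15 of 45% (placebo) and 70% (sarilumab); about 80 and 160 patients per comparison; log-rank test, two-sided 0.05; stated power at least 90%.

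**Assumptions, not in the documents.** Exponential times; follow-up cut at Day 29; a departure hazard equal in both arms. Let q be the share who would leave unimproved by Day 29 if nobody improved. Deaths and rescue are ignored.

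**Step 1, the plan's own figure.** Daily hazard λ = −ln(1−p)/15, which is 0.03986 for placebo and 0.08026 for sarilumab. HR = ln 0.30 / ln 0.55 = 2.01. Events by Day 29 = 80(1−e^(−29×0.03986)) + 160(1−e^(−29×0.08026)) = 54.8 + 144.4 = 199.2. Schoenfeld power = Φ(√(199.2×2/9) × ln 2.014 − 1.96) = Φ(2.70) = 99.7%. Counting only the 148 events by Day 15 gives 98.0%. The more conservative Freedman form gives 93.4% at Day 15 and 98.1% at Day 29. The stated 90% is reproduced as a lower bound; 97 events would suffice for it.

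**Step 2, equal departures under the present rule.** μ = −ln(1−q)/29, which is 0.00177 at 5% and 0.00363 at 10%. Apparent HR = (0.08026+μ)/(0.03986+μ). Departures counted as events in an arm of n patients = n × μ/(λ+μ) × (1−e^(−29(λ+μ))).

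| q by Day 29 | HR | Events | Departures (placebo + sarilumab) | Power |
|---|---|---|---|---|
| 0% | 2.01 | 199.2 | 0 | 99.7% |
| 2% | 2.00 | 200.0 | 1.0 + 1.2 = 2.2 | 99.6% |
| 5% | 1.97 | 201.3 | 2.4 + 3.1 = 5.5 | 99.5% |
| 10% | 1.93 | 203.3 | 4.8 + 6.3 = 11.1 | 99.3% |
| 15% | 1.89 | 205.3 | 7.2 + 9.6 = 16.8 | 99.0% |

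**Step 3, unequal departures.** Suppose no true effect, with departures in the sarilumab arm only. Apparent HR = (0.03986+μ)/0.03986. At q = 5% this is 1.04 and the two-sided rejection probability is 5.8%. At 10% it is 1.09 and 8.3%.

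**Step 4, what the fix does to power.** This was simulated at a heavier rate, 10% by Day 15, which is 1−0.9^(29/15) = 18.4% by Day 29 (3,000 trials; departures kept at risk to Day 29 as non-events). Mean events fall from 206.7 to 186.1, the HR rises from 1.86 to 1.92, and power is 98.5% under both rules.

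**The case against.** Four arguments have weight.

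1. *A transfer may not be a discharge at all.* The missing-data paragraph of SAP 2.4.4.1 treats a patient who is alive and not discharged as still hospitalized. On that wording a site could record a transferred patient as not discharged, and no false event would arise. This stands, and it is why the point is conditional on how the eCRF records the departure.

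2. *For hospice, the plan follows its own convention.* The patient does fit the label of level 7, the protocol expressly deems early discharge an improvement, and the key secondary endpoint captures later deaths. So for hospice there is no contradiction in the text. What remains is that leaving without improving is not an improvement, and the key secondary does not undo the primary event.

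3. *The numbers are small.* Equal rates pull the HR towards 1, and power is untouched. This stands; the case for change is the validity of the event.

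4. *The fix misclassifies too.* A patient at baseline level 4 needs level 6 or 7. If transferred at level 5 and sent home days later with no dated record, that patient becomes a non-event. The Day 29 call (Protocol 1.3 and 4.1) is not stated to yield a dated score. The fix also censors this group at Day 29, while other non-improvers are censored at their last observation. Both are real costs. In Step 4 the fix recovers less than half of the dilution: 1.86 to 1.92, against 2.01 with no departures.

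A reader might also infer from exclusion E 01 that the protocol expects such departures. It does not show this: it excludes patients unlikely to remain at the site beyond 48 hours but gives no reason for leaving, and quick recovery fits equally well.

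**Conclusion.** The point holds in conditional form and should be fixed. Both documents make any live discharge a primary event. If acute-hospital transfers or hospice discharges are recorded as discharges, unimproved patients without earlier rescue become primary successes. For transfers the imputed score contradicts the scale.

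The size rests on assumed rates. With equal rates of 5% or 10% by Day 29 absent improvement, about 6 or 11 of roughly 200 events are departures. The HR is 1.97 or 1.93 instead of 2.01, and power stays well above 90%. Setting the same percentages at Day 15 would make the problem look larger, because 5% and 10% by Day 15 mean 9.4% and 18.4% by Day 29.

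Two stronger conclusions are tempting but unsupported. One is that the rule biases the trial towards sarilumab: Step 3 shows that one-sided departures could do so, but nothing in the documents suggests unequal rates, and blinding makes them less likely. The other is that the trial is underpowered because of the rule; Steps 2 and 4 show that it is not at the design effect.

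**What to change.** Before unblinding for the primary analysis, state in SAP 2.4.4.1 and Protocol 9.4.2 that a departure whose recorded reason is transfer to another acute hospital or discharge to hospice is not by itself an event and is not scored 7. Use later dated status where it exists. Otherwise treat the patient as a non-event censored at Day 29, the date Protocol 9.4.2 already uses for deaths, and not at departure. Censoring at departure, which the SAP's last-observation wording could give, would probably be informative. Leave rescue censoring as it is. Say which score applies to these patients in secondary endpoints 1 and 2.

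Keep the present all-discharges-as-events rule as a sensitivity analysis, so that the effect of the choice is visible.

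The cost is one rule, one derivation and one extra analysis, plus a data query if the eCRF does not separate these reasons. A few events are lost: up to about 6 or 11 at the assumed 5% or 10%, if no later status is known. Some transferred patients who later recover without a dated status will count as non-events.
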